| Study Description: | 
Major depression in mid- and late-life is characterized with abnormalities in the Positive Valence System (PVS). Exposure to rewarding experiences can target these abnormalities and in turn, reduce depression severity. Given the high prevalence of loneliness and social isolation in late life, socially rewarding interactions are especially important. Engagement in social interactions with significant others during reward-based psychotherapy reduces depression and increases behavioral activation. The aim of the study is to examine if exposure to meaningful social rewards during psychotherapy, engages PVS circuitry and improves mid- and late-life major depression. The "reward exposure" of this study will consist of meaningful social activities with significant others ("Engage & Connect"). The study will be a pilot RCT that will compare 9-week "Engage & Connect" vs. a Symptom Review and Psychoeducation condition (SRP) for adults older than 50 years with major depression. We will investigate changes in resting-state functional connectivity, social reward processing during an fMRI-based social reward task, and changes in behavioral outcomes over the course of treatment.
 |
| Sample Size: | N= 60 |
| Enrollment: | This study will enroll 60 subjects and screen up to 90 subjects. |
| Study Population: | Individuals aged 50-85 with major depression |
| Enrollment Period: | The study will recruit participants over 5 years |
| Study Design: | 
This is a randomized controlled trial comparing two psychosocial interventions. We will assess target engagement of the PVS through functional connectivity at rest (rsFC), a self-report measure of behavioral activation (BADS), and performance on a novel fMRI social reward paradigm, during two psychotherapies for middle-aged and older adults with major depression, i.e., "Engage & Connect" therapy (n = 30) and a comparison condition of Symptom Review and Psychoeducation (SRP; n = 30). Participants will receive nine weekly therapy sessions. We will administer research assessments at baseline, Weeks 3, 5, and 9 and MRI scans at baseline, Week 5 and 9. All participants will provide informed consent prior to enrolling in the study.
 |
| Description of Sites/ Facilities Enrolling | |

| | |
|----------------------------------|---|
| Participants: | Participating sites will be the Weill Cornell Medicine Psychiatry Department in Manhattan and the Weill Cornell Institute of Geriatric Psychiatry in Westchester. |
| Study Duration: | July 31, 2027 |
| Participant Duration: | Participation duration is estimated for approximately 9 weeks, which is the duration of the psychosocial intervention provided. Study enrollment is expected to last 5 years; we propose an additional 2 years for data analysis and manuscript preparation. The projected end date of this study is July 31, 2027. |
| Study Agent/Device Name | |
| Intervention Description: | Participants will be randomized to one of two psychosocial interventions, each consisting of 9 weekly sessions: 1) “Engage & Connect” – a reward-based psychotherapy aimed to increase engagement in rewarding social activities; 2) Symptom Review and Psychoeducation (SRP) aimed to track patients’ depressive symptoms and provide education regarding depression. |
| Primary Objective: | The principal aim of this pilot study is to examine if exposure to meaningful social rewards during psychotherapy engages reward circuitry and improves mid- and late-life major depression. We will test whether “Engage & Connect” leads to: 1) increase in resting state functional connectivity of the Positive Valence System (PVS) |
| Secondary Objectives: | We will test whether “Engage & Connect” leads to: 2) increase in behavioral activation (BADS scale); 3) reduction in depression severity (MADRS scale) |
| Exploratory Objectives: | Evaluate whether in “Engage & Connect” treated participants, change in rsFC of the PVS and behavioral activation (BADS) predicts subsequent reduction in depression severity (MADRS). Investigate changes in social reward processing over the course of psychotherapy using a novel Social Incentive Delay (SID) fMRI task |
| Primary Endpoints: | Change in resting state functional connectivity of the PVS over 9 weeks; |
| Secondary Endpoints: | Change in BADS scores and MADRS scores over 9 weeks |

1.1 Schema

*The time point(s) indicated in the schematic should correspond to the time point(s) in **Section 6.1, Schedule of Assessments**, e.g., Visit 1; Visit 2; etc.*

Note. 60 patients will be randomly assigned to 9-weeks of either “Engage & Connect” (N=30) or “SRP” (N=30); BADS = Behavioral Activation for Depression scale; MADRS = Montgomery-Asberg Depression Rating Scale; rsFC = resting state functional connectivity; PHQ9 = Patient Health Questionnaire; SID Task = Social Incentive Delay Task

1.2 Study Objectives and End Points

1.2.1 Primary Objectives

Examine if exposure to meaningful social rewards during psychotherapy, engages reward circuitry and improves mid- and late-life major depression. The “reward exposure” of this study will consist of meaningful social activities with significant others (“Engage & Connect”). We will test whether “Engage & Connect” leads to change in resting state of the PVS over 9 weeks. The study will be a pilot RCT that will compare 9-week “Engage & Connect” vs. a Symptom Review and Psychoeducation condition (SRP) for adults 50-85 years old with major depression

1.2.2 Secondary Objectives

We will test whether “Engage & Connect” leads to: 2) increase in behavioral activation (BADS scale); 3) reduction in depression severity (MADRS scale).

1.2.3 Exploratory Objectives

Evaluate whether in “Engage & Connect” treated participants, change in rsFC of the PVS and behavioral activation (BADS) predicts subsequent reduction in depression severity (MADRS).

Investigate changes in social reward processing over the course of psychotherapy using a novel Social Incentive Delay (SID) fMRI task

1.2.4 Primary Endpoints

Change in resting state functional connectivity of the PVS over 9 weeks.

1.2.5 Secondary Endpoints

Change in BADS scores and MADRS scores over 9 weeks.

2. Background

2.1 Disease

Depression in late life is common¹ and associated with suffering, reduced quality of life,² increased risk of cognitive dysfunction,³ dementia,⁴ disability, cardiac, cerebrovascular, peripheral diseases,⁵ suicidality, all-cause mortality,^{6,7} and economic burden.⁸

2.2 Investigational Agent/Device, or Surgical Treatment/Method

Antidepressants have modest efficacy in late-life depression.^{9,10} The public health impact of antidepressants is attenuated by poor adherence, inadequate dosages and duration, and infrequent follow up of older patients, most of whom are treated in primary care practices.^{11,12} Psychotherapies are efficacious in late-life major depression¹³⁻¹⁵ and well-liked by older adults.^{16,17} However, too few community therapists are able to offer evidence based psychotherapies, mainly because of their complexity.¹⁸⁻²¹ Therefore, there is a need for streamlined efficacious psychotherapies that can match the skill set of community therapists.

Our group developed “Engage”, a streamlined, stepped psychotherapy for mid- late-life depression, whose principal intervention is “reward exposure”.²² In patients with negativity bias, apathy, or inadequate emotional regulation interfering with “reward exposure”, “Engage” offers additional interventions so that “reward exposure” proceeds unimpeded. “Engage” is based on the view that dysfunction of Positive Valence Systems (PVS) perpetuates late-life depression.²²

“Engage” reduces late-life depression and disability.^{23,24} Early increase in resting state functional connectivity (rsFC) in PVS structures during “Engage” predicts increase in behavioral activation.²⁵ Change in behavioral activation is followed by reduction of depressive symptoms.²⁶ In order to further streamline “Engage” and guide its personalization, we examined whether specific types of “reward exposure” have higher therapeutic value. Activities involving social interactions with significant others (but not solitary activities) predicted subsequent increase in behavioral activation and reduction of depression.²⁷ We have also documented that high perceived social support predicts early response to psychotherapy.²⁸ Exposure of socially isolated older adults to social rewards during “Engage” led to greater reductions of depression than a ‘care as usual’ condition.²⁹ The above findings underscore the therapeutic role of rewarding social interactions with significant others. Based on this work, we developed “Engage & Connect”, a streamlined version of “Engage”, whose principal intervention is exposure to meaningful, rewarding social activities with significant others. “Engage & Connect” aims to recondition PVS functions, increase behavioral activation, and lead to reduction of symptoms of depression.

2.3 Rationale

The proposed study will be the first study to test target engagement of “Engage & Connect”, a social reward-focused intervention for mid- and late-life depression. “Engage & Connect” is innovative because: 1) It is directly informed by neurobiological research and designed to address dysfunction of PVS, a core component of depression; 2) It is based on data

demonstrating that exposure to social rewards has the highest probability to improve depressive symptoms; 3) It is streamlined so that it can potentially be used by community clinicians. The NIMH Strategies 3.1; 3.2 encourage the development of novel streamlined treatments informed by advances in neuroscience.

To our knowledge, the proposed study will be the first to examine neural processing of social rewards in mid- and late-life depression. It is based on computational modeling, which identified perceived social support as the strongest predictor of early response to psychotherapy and examines whether PVS changes by mid-treatment predict response of depression to “Engage & Connect”. Along with other PVS function measures, it uses a novel social reward fMRI paradigm to examine PVS change and its relationship to “Engage & Connect” response. Behavioral tasks and clinical scales across multiple units of analysis are quick, cost-effective, and easy to administer, making them feasible to use in future large-scale studies and as screening tools in clinical settings.

2.4 Risk/Benefit Assessment

2.4.1 Known Potential Risks

Participants and family/caregivers participating in this study may be exposed to the following risks:

1. The burden of responding to standardized assessments.
2. The distress associated with discussing personal concerns with research personnel.
3. The discomfort of an MRI scan (approximately 60 minutes per session).
4. Worsening of patients' depression.
5. Skin irritation from the optional study wearable device (smartwatch).
6. Suicide risk.

2.4.2 Known Potential Benefits

Enrolled participants will accrue the following benefits at no cost:

1. A structured evaluation of psychopathology and an assessment of functional limitations for which interventions are needed.
2. Nine weekly sessions of psychotherapy intervention aimed to reduce depression severity.
3. Ongoing monitoring of clinical status and appropriate referral for clinical care in the event of deterioration.

Additionally, some participants find research participation to be a meaningful experience.

2.4.3 Assessment of Potential Risks and Benefits

The risks for study participants are minimal. We anticipate that a portion of the participants will benefit from the psychotherapies delivered in our study and experience improvement in depression severity. Additionally, the potential knowledge to be gained in this study and its clinical implications are substantial. The study could provide evidence for a novel streamlined social reward-based psychotherapy which targets

network abnormalities central in mid- and late-life major depression and could potentially benefit patients with mid- or late-life depression in the future.

2.5 Correlative Studies Background

NA

3. Study Design

3.1 Overall Design

The aim of the proposed study is to examine whether exposure to socially rewarding activities in a reward-based psychotherapy ("Engage & Connect") leads to changes in Positive Valence Systems (PVS) in middle-aged and older adults with major depression. We will assess target engagement of the PVS through functional connectivity at rest (rsFC), a self-report measure of behavioral activation (BADS), and performance on a novel fMRI social reward paradigm, during two psychotherapies for middle-aged and older adults with major depression, i.e. "Engage & Connect" therapy (n = 30) and a comparison condition of Symptom Review and Psychoeducation (SRP; n = 30). Participants will be randomized to nine weekly therapy sessions. Participants may be asked to use a wearable device during their participation in the study. The device allows for passive sensing of movement (steps), heart rate, and sleep daily. Participants and therapists may be able to review their activity for the week to augment the sessions. We will administer research assessments at baseline, Weeks 3, 5, and 9 and MRI scans at baseline, Week 5 and 9. All participants will provide informed consent prior to enrolling in the study. All participants will be recruited at Weill Cornell Medicine.

The "reward exposure" of this study will consist of meaningful social activities with significant others ("Engage & Connect"). The study will be a pilot RCT that will compare 9-week "Engage & Connect" vs. a Symptom Review and Psychoeducation condition (SRP) for adults older than 50 years with major depression and test the following hypotheses:

During the 9 week course of "Engage & Connect" treatment there will be an:

- H1.** Increase in rsFC of the PVS.
- H2.** Increase in behavioral activation (BADS scale)
- H3.** Reduction in depression severity (MADRS scale).

SH. In "Engage & Connect" treated participants, change in: **SH1a)** rsFC of the PVS and **SH1b)** behavioral activation (BADS) will predict subsequent reduction in depression severity (MADRS). These relationships will not be observed in the SRP treated group. The rationale of this hypotheses is based on the theory that the "Engage & Connect" mechanism of action is reconditioning the PVS, while SRP relies on non-specific mechanisms of action.

3.2 Scientific Rationale for Study Design

The proposed study will be the first study to test target engagement of "Engage & Connect", a social reward-focused intervention for mid- and late-life depression. "Engage & Connect" is innovative because: 1) It is directly informed by neurobiological research and designed to address dysfunction of PVS, a core component of depression; 2) It is based on data demonstrating that exposure to social rewards has the highest probability

to improve depressive symptoms; 3) It is streamlined so that it can potentially be used by community clinicians. The NIMH Strategies 3.1; 3.2 encourage the development of novel streamlined treatments informed by advances in neuroscience.

To our knowledge, the proposed study will be the first to examine neural processing of social rewards in mid- and late-life depression. It is based on computational modeling, which identified perceived social support as the strongest predictor of early response to psychotherapy, and examines whether PVS changes by mid-treatment predict response of depression to “Engage & Connect”. Along with other PVS function measures, it uses a novel social reward fMRI paradigm to examine PVS change and its relationship to “Engage & Connect” response. Behavioral tasks and clinical scales across multiple units of analysis, are quick, cost-effective, and easy to administer, making them feasible to use in future large-scale studies and as screening tools in clinical settings.

3.3 Justification for Dose

Selection of 9 weeks of treatment as “dosage” is based on our previous published work showing that this length of treatment in similar “Engage” psychotherapy studies reduces depressed older adults depression severity and increases their behavioral activation.^{23,26,27}

3.4 End of Study Definition

A participant is considered to have completed the study if he or she has completed all phases of the study including the last visit or the last scheduled procedure shown in the **Schedule of Assessments (SoA), Section 6.1**. The end of the study is defined as completion of the last visit or procedure shown in the SoA in the trial.

4. Subject Selection

4.1 Study Population

We will recruit 60 non-demented middle-aged and older adults (aged 50-85; stratified so that 50% are older than 65) with Major Depressive Disorder (MDD) without psychotic features, determined by the Structured Clinical Interview for DSM-5 (SCID). Based on previous studies we expect a 1.6:1 female: male ratio, reflecting higher rates of major depression among women. We expect an attrition rate of ~10%, comparable to previous “Engage” psychotherapy trials conducted at the Weill Cornell Institute of Geriatric Psychiatry. Included participants will not receive other psychotherapeutic or pharmacological treatments and will either be off antidepressants or will be on a stable dose of antidepressants for ≥ 8 weeks at study entry. We will exclude participants with intent or plan to attempt suicide in the near future, as well as those diagnosed with antisocial or borderline personality disorder (DSM-V); dementia [Mini Mental Status Exam (MMSE) ≥ 1 SD below the mean score for patient’s age and education, or DSM-5 criteria]; delirium, severe or acute medical illness, i.e. metastatic cancer, decompensated organ failure, major surgery, recent stroke, or myocardial infarction.

4.2 Inclusion Criteria

1. Ages aged 50-85 [stratified so that 50% are older than 65]
2. Diagnosis of unipolar major depressive disorder without psychotic features, determined by the SCID
3. Montgomery-Åsberg Depression Rating Scale (MADRS) score ≥ 20 .

4. Mini Mental Status Exam (MMSE) \leq 1 SD below the mean score for patient's age and education
5. Off antidepressants or on a stable dose of an antidepressant for 8 weeks and do not intend to change the dose in the next 10 weeks.
6. Capacity to provide consent for research assessment and treatment.

4.3 Exclusion Criteria

1. Intent or plan to attempt suicide in the near future.
2. History or presence of psychiatric diagnoses other than major depressive disorder without psychotic features, generalized anxiety disorder, persistent depressive disorder, or specific phobia.
3. Use of psychotropic drugs or cholinesterase inhibitors other than use of \leq 0.5 mg of lorazepam daily up to seven times per week.
4. Neurological disorders (dementias, history of stroke, multiple sclerosis, Parkinson's disease, epilepsy, etc.); cardiac, renal, or respiratory failure; severe chronic obstructive pulmonary disease; metastatic cancer; or debilitated states or less common medical illnesses that may either influence brain systems of interest or ability to participate in the study. A senior clinician at the institute will review any medical illnesses that does not appear in the list above and determine whether it interferes with the study of positive valence system functions in depression.
5. Contraindications to MRI scanning including cardiac pacemaker, heart valve replacement, vascular stent, insulin pump, cochlear implant, any other metallic biomedical implant contraindicating to MRI, and claustrophobia.

4.4 Lifestyle Considerations

Not Applicable

4.5 Screen Failures

Screen failures are defined as participants who consent to participate in the clinical trial but are not subsequently randomly assigned to the study intervention or entered in the study. A minimal set of screen failure information is required to ensure transparent reporting of screen failure participants, to meet the Consolidated Standards of Reporting Trials (CONSORT) publishing requirements and to respond to queries from regulatory authorities. Minimal information includes demography, screen failure details, eligibility criteria, and any serious adverse event (SAE).

Individuals who do not meet the criteria for participation in this trial (screen failure) because of low depression severity or exclusion criteria related to recent change in medication may be rescreened. Rescreened participants should be assigned the same participant number as for the initial screening.

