6.1 Schedule of Assessments

Patient participants will be randomized to receive a 9-week course of either weekly Engage & Connect therapy or SRP, and research assessments will be conducted at baseline and weeks 3, 5, and 9.

| Week | Baseline | 1 | 2 | 3 | 4 | 5 | 6 | 7 | 8 | 9 |
|----------------------------|----------|---|---|---|---|---|---|---|---|---|
| Therapy Session | | x | x | x | x | x | x | x | x | x |
| Research Assessment | x | | | x | | x | | | | x |
| MRI Scans | x | | | | | x | | | | x |

Trained research assistants unaware of study hypotheses will collect weekly clinical and self-report ratings at each study time point.

| Instrument | Baseline | Week 1 | Week 3 | Week 5 | Week 9 |
|---|----------|--------|--------|--------|--------|
| Demographics | | | | | |
| Demographic questionnaire | x | | x | x | x |
| Brief Antidepressant Questionnaire (BAQ) | x | | x | x | x |
| Intent to Complete | x | | | | |
| Depression Severity and Anhedonia | | | | | |
| Montgomery Åsberg Depression Rating Scale (MADRS) | x | | x | x | x |
| Hamilton Depression Severity Scale (HAMD) | x | | x | x | x |
| The Dimensional Anhedonia Rating Scale (DARS) | x | | x | x | x |
| Behavioral Activation and Reward Measures | | | | | |
| Behavioral Activation for Depression (BADS) | x | | x | x | x |
| Anticipatory and Consummatory Interpersonal Pleasure Scale (ACIP) | x | | x | x | x |
| Clinical Characteristics | x | | | | |
| Mini-Mental State Examination (MMSE) | x | | | | |
| Interpersonal Problems Inventory – 32 items (IIP-32) | x | | | | x |
| Duke Social Support Index | x | | x | x | x |
| Revised UCLA Loneliness scale | x | | | | x |
| Treatment Rationale Scale | | x | | | |
| MRI tasks | x | | | x | x |
| Probabilistic Reversal Learning task | x | | | x | x |
| Social Incentive Delay task | x | | | x | x |
| Adverse Event Evaluation | | x----- | | | x |

Trained research assistants unaware of study hypotheses will collect weekly clinical and self-report ratings at each study time point via zoom, and in person assessments will be offered if needed.

- **Demographics:** Our demographics questionnaire includes age, gender, race, religion, living conditions, marital status, occupation, birth place, and education.

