6.1.1 Screening Visit + Baseline (*several days before start of treatment*)

Screening will include the Major Depression Module and the Screener from the SCID-V to ensure the participant meets the clinical criteria (see exclusion and inclusion criteria section)

- Informed consent
- Medical history and medication history
- Demographic questionnaire
- Brief Antidepressant Questionnaire (BAQ)
- Intent to Complete
- Depression Severity and Anhedonia
- Montgomery Åsberg Depression Rating Scale (MADRS)
- The Dimensional Anhedonia Rating Scale (DARS)
- Behavioral Activation for Depression (BADS)
- Anticipatory and Consummatory Interpersonal Pleasure Scale (ACIP)
- Mini-Mental State Examination (MMSE)
- Interpersonal Problems Inventory – 32 items (IIP-32)
- Duke Social Support Index
- Revised UCLA Loneliness scale

MRI tasks

- Probabilistic Reversal Learning task
- Social Incentive Delay task

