12.1 Study Design/Endpoints

The principal aim of this pilot study is to examine if exposure to meaningful social rewards during psychotherapy, engages reward circuitry and improves mid- and late-life major depression. The “reward exposure” of this study will consist of meaningful social activities with significant others (“Engage & Connect”). The study will be a pilot RCT that will compare 9-week “Engage & Connect” vs. a Symptom Review and Psychoeducation condition (SRP) for adults older than 50 years with major depression and test the following hypotheses:

During the 9 week course of “Engage & Connect” treatment there will be an:

- H1.** Increase in rsFC of the PVS.
- H2.** Increase in behavioral activation (BADS scale)
- H3.** Reduction in depression severity (MADRS scale).

SH. In “Engage & Connect” treated participants, change in: **SH1a)** rsFC of the PVS and **SH1b)** behavioral activation (BADS) will predict subsequent reduction in depression severity (MADRS). These relationships will not be observed in the SRP treated group. The rationale of this hypotheses is based on the theory that the “Engage & Connect” mechanism of action is reconditioning the PVS, while SRP relies on non-specific mechanisms of action.

To further investigate the PVS correlates of social reward, we developed a social reward fMRI paradigm, modeled after a monetary incentive delay task⁴⁴ and plan to use it in analyses for hypothesis generation.

Analysis Plan

H1, H2, H3: During the 9-week course of “Engage & Connect” there will be an:

- H1.** Increase in rsFC of the PVS
- H2.** Increase in behavioral activation (BADS)
- H3.** Reduction in depression severity (MADRS).

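### The MADRS score that admits a participant is also the first point of the H3 trend, so regression to the mean counts as improvement in a within-arm test

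*Combined protocol and SAP*

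**What the plan says.** Section 4.2 sets the severity threshold: "Montgomery-Åsberg Depression Rating Scale (MADRS) score ≥ 20". Section 6.1.1 describes one combined occasion, "Screening Visit + Baseline", and lists the MADRS once. The instrument table in Section 6.1 has a Baseline column and no screening column; it places the MADRS at Baseline and Weeks 3, 5 and 9.

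Section 4.5 allows a second attempt for people who fail "because of low depression severity or exclusion criteria related to recent change in medication may be rescreened". It gives no maximum number of attempts and no minimum interval, and adds: "Rescreened participants should be assigned the same participant number as for the initial screening". The synopsis states: "This study will enroll 60 subjects and screen up to 90 subjects".

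Sections 3.1 and 12.1 word H3 as a change during Engage & Connect: "Reduction in depression severity (MADRS scale". The model described in Sections 12.1 and 12.4.1 has a random intercept per subject and time terms. Neither section names a treatment or treatment-by-time term for H3, although the trial is randomized against SRP.

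**The concern.** A score that must reach 20 to admit someone is, on average, above that person's usual level, because some people pass on a rating that happens to be high. Weeks 3, 5 and 9 carry no such selection. If the qualifying score is also the baseline, the mean falls afterwards even when nobody has changed. Retesting people who first scored too low adds to this, since they enter on the rating that finally passed.

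MADRS change is a named secondary endpoint, and Section 10.1 makes its slope the response measure. With time terms only, a reader could not separate a fall of a point or so caused by selection from one caused by treatment.

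**Working it through.** **No plan figure to reproduce.** The power analysis text in Section 12.1 lists outcomes and time points. It gives no MADRS mean, SD, reliability or expected change.

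**Inputs from the documents.** Threshold 20; 60 enrolled from up to 90 screened; 30 per arm; attrition about 10%, so 30 × 0.9 = 27 completers per arm; MADRS at Weeks 0, 3, 5 and 9.

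**Assumptions.** Candidate SD 7, reliability r from 0.6 to 0.8, normal scores, independent errors, no true change. First-screen pass rate 60/90 = 0.667, which treats every failure as a low score at a single screen.

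**Fall with one screen.** Expected fall = (1 − r) × SD × φ(c)/(1 − Φ(c)), where c = (20 − mean)/SD.
- A pass rate of 0.667 gives c = −0.431, that is, a candidate mean of about 23.0.
- φ(c)/(1 − Φ(c)) = 0.3636/0.6667 = 0.545.
- r = 0.8: 0.2 × 7 × 0.545 = 0.76 points.
- r = 0.6: 0.4 × 7 × 0.545 = 1.53 points.

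**One rescreen for every low scorer (simulation, 1,000,000 candidates).** The mean fall becomes 0.96 (r = 0.8) or 1.80 (r = 0.6), an addition of 0.20 or 0.28. Those admitted at the second attempt fall by 2.4 or 3.2 points, but they are only about 12% or 17% of entrants. The shared entry and baseline score therefore matters more than rescreening.

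**Effect on a linear time trend.** The mean of 0, 3, 5, 9 is 4.25 and the sum of squares is 42.75. An excess B at baseline alone tilts the slope by 4.25B/42.75 = 0.0994B per week, or 0.895B over nine weeks.
- Apparent nine-week fall: 0.7 points (r = 0.8) to 1.4 points (r = 0.6).
- Slope standard error with 27 participants: SD√(1 − r)/√(27 × 42.75), which is 3.13/33.97 = 0.0922 (r = 0.8) or 4.43/33.97 = 0.130 (r = 0.6).
- Bias over standard error: 0.0759/0.0922 = 0.82, or 0.152/0.130 = 1.17.
- Chance of a significant reduction at two-sided 5% (nominal 2.5% in that direction): P(Z > 1.96 − 0.82) is about 13%; P(Z > 1.96 − 1.17) is about 21%. A simulation of the same setting gave 12% and 21%.

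**Wider assumptions.** With candidate mean 20 to 28, SD 6 to 8 and r 0.6 to 0.9, the one-screen fall runs from 0.1 to 2.6 points, and to 3.0 with one rescreen.

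**Between arms.** Both arms pass the same gate before treatment begins. In simulation the difference between arms in this artefact stayed within 0.03 points.

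**The case against.** The strongest reply is that this is a randomized comparison and the artefact cancels against SRP. That is correct for a between-arm contrast. It does not rescue H3 as written, because the hypothesis and its named model terms concern change over time in Engage & Connect. A reader may say a comparison is implied by the pilot RCT wording and by the covariate rule for imbalance between groups, but no treatment term is stated for H3.

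Second, nothing says outright that the qualifying score is the analysis baseline. It is an inference from one combined visit with one listed MADRS. It is the natural reading, but a separate rating may be intended.

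Third, three stronger readings are tempting and not supported.
- Rescreening is unlimited: Section 4.5 is only silent on number and interval.
- The artefact is typically 2 to 4 points: in the SD 7 setting, a mean above 2 points with one screen needs a candidate mean of about 20, where only 50% pass. The planned 60 of at most 90 points to about 67%. Larger values also describe the minority admitted on a second attempt. The 67% anchor is itself loose: other reasons for failure would raise the severity pass rate and shrink the fall, while entrants admitted on a rescreen would mean a lower first-screen rate.
- The trial's comparison or primary endpoint is biased: it is not, since the artefact is equal in both arms and entry is not selected on rsFC.

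Finally, the rejection rates assume a linear trend, whereas the plan lets BIC choose a higher-order form.

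**Conclusion.** The concern holds for the within-arm MADRS change. On the schedule as written, one score both admits the participant and starts the H3 trend, and the stated test cannot separate regression to the mean from improvement. Its size rests on assumed SD, reliability and pass rate: about 0.8 to 1.5 points under the 67% anchor, plus about 0.2 to 0.3 with one rescreen, and anything from trivial to about 3 points under wider assumptions. This is a modest bias in a secondary endpoint of a pilot, worth correcting because the correction is cheap.

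**What to change.** 1. **Sections 12.1 and 12.4.1.** Base the H3 conclusion on the treatment-by-time contrast with SRP, and label the within-arm change descriptive. This is the step that removes the artefact. It needs no new data. The cost is precision: with equal arms, the standard error of the difference in slopes is √2 = 1.41 times that of one arm.
2. **HAMD sensitivity analysis.** Pre-specify the same H3 model on the HAMD, which is not an entry criterion. This reduces the bias but may not remove it, because two depression ratings at one visit can share the same temporary fluctuation. First reconcile the Section 6.1 table, which schedules the HAMD at Baseline, with the Section 6.1.1 list, which omits it.
3. **Section 4.5.** State a maximum number of rescreens for low severity, flag rescreened participants in the dataset, and report their number by arm. The cost is one sentence, one variable and perhaps a few marginal candidates.
4. **Slope over Weeks 3, 5 and 9.** This leaves out the entry score but should be supportive only. Its time sum of squares is 18.67 against 42.75, so the standard error is √(42.75/18.67) = 1.51 times as large, about 51% more. It also omits the first three weeks of response.
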